6.5. Updosing and Dose Modifications of Study Drug

6.5.1. Updosing and Downdosing of Study Drug

Initial updosing to a new level will be attempted sequentially every 2 weeks per the updosing regimens in Table 3. A telephone call follow-up will be done 1 day after each updosing visit to inquire about allergic symptoms and promote adherence to treatment, and remind subjects to complete the daily diary. As shown in Table 5, subjects who fail to tolerate dose levels of at least 50 mg/day will discontinue study drug; these subjects will remain in the study per Section 7.2.

Subjects who tolerate at least 50 mg/day will continue in the updosing portion of the study, and will return to the clinic every 2 weeks for updosing under direct medical supervision until the randomized target dose of 1500 mg/day (100 mg per food source; low-dose regimen) or 4500 mg/day (300 mg per food source; high-dose regimen) is achieved (Figure 1). If a subject fails 3 updosing attempts to any dose level above 50 mg/day, the site should contact the Study Medical Monitor for further guidance regarding additional updosing. Subjects who are unable to reach the randomized target dose will continue on the highest dose level they are able to reach, as long as the dose of study drug is at least 50 mg.

Subjects who do not tolerate the current dose level may be permitted to downdose to a previous dose level at the discretion of the investigator.

Subjects must not be updosed for 3 days after the cessation of administration of corticosteroids.

For guidance regarding updosing during a public health emergency, refer to Appendix 6 (Section 10.6).

Table 5: Updosing Decisions for Study Drug

Dose Level Attempted during Updosing Phase (mg)	Tolerated Dose within 3 Attempts?	Instructions
5	Yes	Continue to the next dose level.
	No	Discontinue study drug and remain in the study per Section 7.2. An additional subject will be randomized without impacting the overall 2:2:1:1 randomization ratio.
20	Yes	Continue to the next dose level.
	No	Discontinue study drug and remain in the study per Section 7.2.
50	Yes	Continue to the next dose level; subject is eligible to continue the study.
	No	Discontinue study drug and remain in the study per Section 7.2.
Any dose above	Yes	Continue to the next dose level.
50 mg	No	Contact Study Medical Monitor for further instructions.

In-Clinic Observation after Initial Study Drug Administration and Every Updosing

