6.1. General Methods

The following general guidelines will apply to all statistical analyses conducted for this study:

- SAS® version 9.4 or higher will be used.
- Unless otherwise specified, table summaries will be presented by pediatric subjects (≥ 4 to < 18 years old) and all subjects (pediatric and adult subjects combined), treatment group and overall. For the primary and secondary endpoints, the table summaries will be provided for the adult subjects (≥ 18 to ≤ 55 years old) as well. In general, for the purpose of data summaries, treatment group for the outputs would be (Low-Dose ADP101, High-Dose ADP101, Pooled ADP101 and Pooled Placebo)
- In general, continuous variables will be summarized using the descriptive statistics for the number of subjects (n), mean, standard deviation (SD), median, minimum (min), and maximum (max). The min and max values will be presented to the same number of decimal places as the raw data. The means and medians will be presented to one more decimal place than the raw data. The SD will be presented to two more decimal places than the raw data. If the raw data has 3 decimal places or more, 3 decimal places will be presented for mean, median, min and max, and SD. The use of other descriptive statistics will be noted where applicable.
- Categorical variables will be summarized using number of subjects or frequency (n) and percentages of subjects. All percentages will be presented with 1 decimal place. Percentages equal to 100% will be presented as 100%, and percentages will not be presented for zero counts. The categories whose counts are zero will be displayed for the sake of completeness. The percentages will be based on total number of subjects in the specified study analysis set under each treatment group (N), unless stated otherwise in the table shell.
- All relevant subject data will be included in listings. All subjects entered into the database will be included in subject data listings. Unless otherwise specified, the listings will be sorted by treatment group, subject number, and assessment date (and time) if applicable.

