6.6. Data Pooling

In general, data for the 2 placebo treatment groups (low/high dose) will be pooled together, and compared to the low- and high-dose ADP101 treatment groups.

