7.8.3.10. Maintenance Dose for Study Drug

The maintenance dose (mg/day) will be summarized by treatment group using descriptive statistics (median, min, max, and Q1:Q3). The number and percentage of subjects whose maintenance dose is 50, 100, 200, 400, 700, 1000, 1500, 3000, or 4500 mg/day will be provided as well. If a subject exits the study prior to achieving a dose of at least 50 mg, then the maintenance dose will be set to missing.

The time to achieving the maintenance dose level is defined as [(first dose date of maintenance dose) – (first dose date of study drug) + 1]. The maintenance dose for these individuals can be determined once the subject has started the exit challenge procedure (i.e. maintenance is the week 38 dose level), reached the target dose for their randomized treatment group or discontinued the study. The time to achieving first maintenance dose will be presented for the treatment period using Kaplan-Meier (KM) method. Subjects who do not reach a maintenance dose will be censored at the date of their last study drug dose. KM curves will be plotted separately for the pooled placebo, low-dose and high-dose groups. A similar method will be repeated for time to achieving target dose level (1500 mg/day for low-dose and 4500 mg/day for high-dose) as maintenance dose.

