7.8.3.11. Target Attainment

100% target attainment occurs when a subject attains the randomized target dose of 1500 mg/day for low-dose regimen or 4500 mg/day for high-dose regimen. A subject's target attainment at MD is expressed as a percentage, calculated as [(maintenance Dose) / (target dose level) × 100].

The number and percent of subjects who attained randomized target levels of 1500 mg/day (low-dose regimen) or 4500 mg/day (high dose regimen) by visit will be provided. The target attainment at MD will be summarized using continuous and categorical (e.g., 100%, $\geq 90\%$ - < 100%, $\geq 80\%$ - < 90%, < 80%) descriptive statistics. The proportion of subjects with 100% target attainment versus visit along with CI will be plotted. A swimmer plot showing individual exposure to study drug (in weeks) over time by treatment group and dose level, will also be provided.

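### The time-to-dose curves in SAP 7.8.3.10 use one pooled placebo group although its two halves have different target doses, so placebo differs from each ADP101 arm even when tolerability is identical

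*SAP*

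**What the plan says.** SAP 7.8.3.10 defines time to maintenance dose from the first dose of study drug and presents it by Kaplan-Meier: "KM curves will be plotted separately for the pooled placebo, low-dose and high-dose groups". It then adds: "A similar method will be repeated for time to achieving target dose level (1500 mg/day for low-dose and 4500 mg/day for high-dose) as maintenance dose". The event in that second analysis is thus a different dose in each regimen.

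SAP 7.8.3.11 measures each subject against his or her own target: "100% target attainment occurs when a subject attains the randomized target dose of 1500 mg/day for low-dose regimen or 4500 mg/day for high-dose regimen". It asks for "The number and percent of subjects who attained randomized target levels of 1500 mg/day (low-dose regimen) or 4500 mg/day (high dose regimen) by visit" and says "The proportion of subjects with 100% target attainment versus visit along with CI will be plotted". It does not name the display groups. Two general rules would then apply. SAP 6.1 says that, in general, "treatment group for the outputs would be (Low-Dose ADP101, High-Dose ADP101, Pooled ADP101 and Pooled Placebo"). SAP 6.6 says that, in general, "data for the 2 placebo treatment groups (low/high dose) will be pooled together".

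The schedule comes from the protocol. Section 6.5.1 states "Initial updosing to a new level will be attempted sequentially every 2 weeks per the updosing regimens in Table 3", and Table 3 gives the high-dose regimen two levels (3000 and 4500 mg) that the low-dose regimen does not have. Randomization is 2:2:1:1, so placebo is split equally between the regimens: 10 and 10 children in SAP Table 1.

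**The concern.** Pooling placebo is reasonable for the food-challenge outcome. It is a different matter when the outcome is itself a dose level or the time taken to reach one. A placebo subject in the high-dose regimen has two more steps to climb than one in the low-dose regimen, whatever he or she tolerates. A pooled placebo curve mixes the two climbs and matches neither ADP101 arm.

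A reader compares the ADP101 curves with placebo to see how much active drug slows escalation. Here the titration schedule alone would place low-dose ADP101 ahead of placebo and high-dose ADP101 behind it. In a study meant to help choose between the two regimens, that pattern could be misread as a tolerability difference.

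The time-to-maintenance curve has a second difficulty. Any level from 50 mg upwards can be a maintenance dose, so a subject who stops climbing early at a low level has an earlier event than one who goes on to target. A faster curve is not necessarily a better one.

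**Working it through.** **Inputs.** Protocol Table 3 levels: 5, 20, 50, 100, 200, 400, 700, 1000, 1500, 3000 and 4500 mg. One step every 2 weeks (Protocol 6.5.1), starting at 5 mg on Day 1. Updosing allowed through Week 38 (Protocol 4.1). Placebo half low and half high regimen (SAP Table 1).

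**The plan's own figure.** The only stated figure that depends on this schedule is a maintenance portion of 2 to 22 weeks (SAP 3.1, Protocol 4.1). Counting to Week 40 gives a maximum of 40 − 16 = 24 weeks (low) and 40 − 20 = 20 (high), with a minimum of 40 − 38 = 2. Counting to Week 38 gives 38 − 16 = 22 and 38 − 20 = 18, but the minimum is then 0. Starting 2 weeks after the first target dose gives 40 − 18 = 22 (low) and 40 − 22 = 18 (high). No single convention gives 2 to 22, so that range should be reconciled with Table 3. The 4-week difference between regimens is the same under each convention (24 − 20, or 22 − 18).

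**Earliest attainment.** Day = (number of levels − 1) × 14 + 1.
- 1500 mg is the 9th level: 8 × 14 + 1 = Day 113 (Week 16).
- 4500 mg is the 11th level: 10 × 14 + 1 = Day 141 (Week 20).

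**Curves under equal tolerability.** Let q be the chance that a 2-weekly attempt succeeds, the same for ADP101 and placebo and for every level. This is an assumption, with range 0.6 to 1. Attempts continue after a failure and there is no downdosing. Then

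P(target by Week w) = P(Binomial(w/2, q) ≥ s), with s = 8 (low) or 10 (high),

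and pooled placebo is the mean of the two. Example for q = 0.9 at Week 18: low = 9 × 0.9⁸ × 0.1 + 0.9⁹ = 0.77; high = 0, since only 9 attempts have been made; pooled placebo = 0.39; gap ±39 points.

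| q | Week of largest gap | Low-dose ADP101 | Pooled placebo | High-dose ADP101 | Gap (points, before rounding) | Median weeks, low / pooled placebo / high |
|---|---|---|---|---|---|---|
| 1.0 | 16 to 18 | 100% | 50% | 0% | ±50 | 16 / 16 / 20 |
| 0.9 | 18 | 77% | 39% | 0% | ±39 | 18 / 20 / 22 |
| 0.8 | 20 | 68% | 39% | 11% | ±29 | 20 / 22 / 24 |
| 0.7 | 24 | 72% | 49% | 25% | ±24 | 22 / 26 / 28 |
| 0.6 | 28 | 69% | 49% | 28% | ±21 | 26 / 30 / 32 |

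At q = 1 the gap is 0 from Week 20. At Week 38 it is about 0 for q of 0.8 or more, 1 point for q = 0.7 and 8 points for q = 0.6. If in addition a share c of subjects in every arm tolerates 1500 mg but never 4500 mg (a further assumption, c = 10% to 30%), a lasting gap of c/2 = 5 to 15 points remains in each direction.

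**After the split.** With placebo shown by regimen, both curves in each pair have the same s, so the expected gap is 0 at every visit for every q. Pooled ADP101 against pooled placebo also gives 0, because both are 1:1 mixtures of the regimens.

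**Time to maintenance dose.** On the simplest reading, a subject who stays at 50 mg (third level) from Week 4 has an event at 2 × 14 + 1 = Day 29, against Day 113 or Day 141 for one who climbs every step to target. SAP 6.2.3 starts maintenance at the run of maintenance doses closest to the exit challenge. On that reading, failed attempts at Weeks 6, 8 and 10 (assumption) would move the start to about Week 10. That is still before Week 16.

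**The case against.** The strongest case on the other side has five parts.

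- **Scope.** Only 7.8.3.10 names a pooled placebo group. A reader might infer that 7.8.3.11 pools as well, but it does not say so. Sections 6.1 and 6.6 are both qualified as general rules, and the table shells are in a separate document. The default columns in 6.1 also include pooled ADP101, whose contrast with pooled placebo is free of the artefact. This stands, and the point on 7.8.3.11 is therefore conditional. It does not rescue the curves in 7.8.3.10, where no pooled ADP101 curve is planned.
- **Size.** The 50-point gap needs every subject to pass every step, and it ends at Week 20. This stands. With imperfect titration the gap is smaller but lasts longer.
- **Importance.** One might infer that these displays are the main evidence on whether each regimen can be reached. The documents do not support that. The ADP101 curves themselves are unchanged by placebo pooling. The SAP also plans counts at each maintenance level, exposure by dose level, unsuccessful dose increases, target-reached subgroups and a swimmer plot. Protocol 9.4.3 ties dose selection to Fisher's exact test on the efficacy endpoints. This stands, although none of those outputs is specified with a regimen-matched placebo time curve.
- **Time to maintenance dose.** The SAP already plans time to target and designates no headline display, so asking to drop the maintenance curve would be a preference. The Day 29 figure depends on how the start of maintenance is read. Both stand. The ordering problem remains on either reading.
- **Precision.** Splitting leaves about 10 children per placebo curve. True, but the pooled curve gains its numbers by mixing two different events.

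**Conclusion.** The point holds for the Kaplan-Meier displays in SAP 7.8.3.10, and conditionally for the by-visit display in 7.8.3.11. The 4-week difference in earliest attainment follows directly from Protocol Table 3 and the 2-week interval. With identical tolerability, pooled placebo lies between the two ADP101 arms. The size and duration of the gaps rest on the assumed common success rate per attempt and on equal placebo halves; only the tolerability-ceiling variant leaves a lasting gap at every success rate.

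The signs are opposite for the two doses, so the artefact flatters the low dose and penalizes the high dose relative to placebo. It does not make ADP101 as a whole look better or worse. Nothing here touches the primary or secondary efficacy analyses, and no test is planned on these displays. It is a modest correction to exploratory output.

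**What to change.** In SAP 7.8.3.10, state an exception to 6.6: plot low-dose ADP101 with low-dose placebo, and high-dose ADP101 with high-dose placebo, for both time to maintenance dose and time to target dose. Make the same exception in 7.8.3.11 wherever the general defaults would otherwise pool placebo.

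Optionally, add time to a common level of 1500 mg/day. Every arm takes the same 8 steps to that level, so all placebo can be pooled there without the artefact.

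Show time to maintenance dose by the level attained, so that an early plateau is not read as quick success, and state which date starts the maintenance sequence after a failed updose.

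The cost is SAP wording and figure shells. The statistical price is about 10 children per placebo curve instead of about 20, in descriptive displays.

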7.8.3.11. Target Attainment

100% target attainment occurs when a subject attains the randomized target dose of 1500 mg/day for low-dose regimen or 4500 mg/day for high-dose regimen. A subject's target attainment at MD is expressed as a percentage, calculated as [(maintenance Dose) / (target dose level) × 100].

The number and percent of subjects who attained randomized target levels of 1500 mg/day (low-dose regimen) or 4500 mg/day (high dose regimen) by visit will be provided. The target attainment at MD will be summarized using continuous and categorical (e.g., 100%, $\geq 90\%$ - < 100%, $\geq 80\%$ - < 90%, < 80%) descriptive statistics. The proportion of subjects with 100% target attainment versus visit along with CI will be plotted. A swimmer plot showing individual exposure to study drug (in weeks) over time by treatment group and dose level, will also be provided.

7.9. Safety Analysis

All safety analyses will be performed using the Safety Population. Safety data in this study will include AEs, clinical laboratory data, vital signs, pulse oximetry, spirometry, physical examinations, and assessment of asthma severity using NHLBI criteria.

Unless otherwise noted, safety data will be summarized descriptively by treatment group for pediatric subjects and all subjects. Further breakdown by Screening Period, Pre-maintenance Period, Maintenance Period, Exit DBPCFC during challenge and Exit DBPCFC off challenge, EOT and Follow-Up Period will be provided for some AE summaries.

7.9.1. Adverse Events

All AEs will be coded and classified according to MedDRA version 23.0 or later. All nonallergic AEs will be graded according to the NCI CTCAE Version 5.0. All allergic AEs will be graded according to the Consortium of Food Allergy Research (CoFAR) grading scale, with Grade 1 (mild symptoms), Grade 2 (moderate symptoms), Grade 3 (severe symptoms), Grade 4 (life-threatening symptoms) and Grade 5 (death). The relationship of AE to study drug will be judged by the investigator as related or not related.

Treatment-emergent AEs (TEAE) are defined as any event that starts or worsens in severity on or after the first dose of study drug until 30 days after the last dose of study drug. TEAEs will be considered treatment-related if relationship information is missing. Similarly, TEAEs will be considered severe if the severity information is missing. Imputed values for relationship, severity or onset date will be used for incidence summaries, while the actual values will be used in data listings. The AEs not considered to be a TEAE will be included in subject listings, but not summarized.

The AESIs include the following categories: anaphylaxis, any AE leading to the use of epinephrine (e.g., EAI), and Eosinophilic Esophagitis (EoE).

All reported AEs will be classified into SOC and PT. Summaries will be ordered by descending incidence of SOC and PT within each SOC for the overall column. Summaries displayed by PT only will be ordered by descending incidence of PT for the overall column. In addition, exposure adjusted incidence rates of TEAEs, treatment-emergent serious adverse events (TESAEs) and treatment-emergent AESIs will be presented, where exposure incidence rate is defined as the total number of events divided by the total number of subject-years at risk during the study treatment period, or defined as the total number of events divided by the total number of study drug doses received during the study treatment period.

An overview summary of the number and percentage of subjects with at least one of the following AE categories will be presented by treatment group and overall.

- Any TEAE
- Any TESAE
- Any TEAE related to study drug

- Any TEAE due to accidental exposure
- Any TEAE due to food challenge
- Any TEAE due to other study procedure
- Any TESAE related to study drug
- Any TESAE due to accidental exposure
- Any TESAE due to food challenge
- Any TESAE due to other study procedure
- Any TEAE resulting in drug discontinuation
- Any TEAE resulting in drug interruption
- Any TEAE resulting in drug modification (i.e., dose decrease or increase)
- Any TEAE resulting in discontinuation from study
- Any TEAE with fatal outcome
- Any allergic TEAE
- Any allergic TEAE with Grade ≥ 3
- Any nonallergic TEAE with Grade ≥ 3
- Any AESI

The number and percentage of subjects with TEAEs/AEs will be summarized by SOC and PT for the following:

- TEAEs
- TEAEs by severity
- Allergic TEAEs
- Allergic TEAEs by severity
- Allergic TEAEs with CoFAR Grade 3 or higher
- Non-allergic TEAEs
- Non-allergic TEAEs by severity
- Non-allergic TEAEs with CTCAE Grade 3 or higher
- TEAEs related to study drug
- TEAEs due to accidental exposure
- TEAEs due to accidental exposure by severity
- AEs due to food challenge (at Screening and Exit DBPCFCs)
- TESAEs
- TESAEs related to study drug
- TEAEs resulting in study drug discontinuation
- TEAEs resulting in discontinuation from study
- Treatment-emergent AESIs by category

In addition, summaries of the following exposure-adjusted rates (per person-years and per total doses) will be provided:

- Exposure adjusted rates of TEAEs by PT
- Exposure adjusted rates of TEAEs related to study drug by PT

- Exposure adjusted rates of TESAEs by PT
- Exposure adjusted rates of treatment-emergent AESIs by PT
- Exposure adjusted rates of treatment-emergent AESIs related to study drug by PT

Subjects will be counted only once within each SOC and PT in the summary tables. For the summary tables by Grade ≥ 3 , if the same TEAE (PT) is reported more than once for the same patient, the highest severity grade will be counted in the summary table.

The following AEs will also be summarized by study period with each AE counted once in the period where it started. The number of subjects with ongoing AEs in each period will be provided as well.

- Overall summary of AEs
- AEs by SOC and PT
- Allergic TEAEs with CoFAR Grade 3 or higher
- AESIs by SOC and PT
- Exposure adjusted rates of TEAEs by PT
- Exposure adjusted rates of treatment-emergent AESIs by PT

The subjects with any CoFAR grade ≥ 3 anaphylaxis and with any CoFAR grade ≥ 4 anaphylaxis will be presented in all AESI summary tables.

The following AEs will be presented as listings by subject:

- Nonallergic AEs
- Allergic AEs
- Serious AEs
- AEs resulting in study drug discontinuation, interruption, or modification
- AEs resulting in study discontinuationAESIs
- AEs with fatal outcome

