In order to obtain results before the Week 40 assessments begin, subjects will have an expanded study visit at Week 38. SPTs will be performed for all 15 foods. Foods that were determined to be a Non-reactive Food at Screening will be reevaluated to assess for development of a potential new FA during the treatment period. Each Non-reactive Food at Screening will be assessed for any new clinical symptoms resulting from the food source; SPT results will also determine which additional foods, if any, will get an Exit DBPCFC, per [Figure 4](#). Only positive results on the DBPCFC will define a new FA developed during the treatment period.

Subjects will continue on study drug during the Exit DBPCFC period, but the daily study drug dose will be withheld on the day of the DBPCFC (\pm additional days per investigator judgment).

End of Treatment: After the final Exit DBPCFC, all subjects will continue to receive study drug at their maintenance dose for up to 4 weeks in a blinded treatment extension period, followed by the End of Treatment (EOT) visit, in order to maintain the blind during subject-level data cleaning. Thereafter, eligible subjects (taking either ADP101 or placebo) who complete the study (through EOT) will be unblinded in a rolling order and assessed for eligibility for the ADP101 open-label extension (OLE) study (under a separate protocol [ADP101-MA-02] and informed consent/assent).

Follow-Up Period: Subjects who are ineligible for or do not wish to continue to the OLE will receive instruction by the investigator about withdrawal from study drug and attend a follow-up visit 14 days from the EOT visit.

Throughout the study, subjects will undergo safety and efficacy assessments as specified in the Schedule of Activities ([Appendix 1](#)). Unscheduled visits can be conducted at any time during the study, as clinically indicated. Over the duration of the study, subjects should continue to avoid foods in their diet to which they are reactive (at any level).

Details of study assessments and procedure conducted during the study are provided in the protocol Section 8 “STUDY ASSESSMENTS AND PROCEDURES.”

Figure 1 Study Schema

[figure not shown]
[figure not shown]
[figure not shown]

Figure 2 Screening Evaluation to Determine Individual Food DBPCFC Testing

[figure not shown]
Abbreviations: DBPCFC = double-blind, placebo-controlled food challenge; SPT = skin-prick test.

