4.4. Exploratory Endpoints

The exploratory endpoints of the study are:

- Change from baseline in eliciting dose of each individual Reactive Food at the Exit DBPCFC
- Changes from baseline in biomarkers, including, but not limited to, specific immunoglobulin E (sIgE) and specific immunoglobulin G subclass 4 (sIgG4), of all foods contained in ADP101
- Change from baseline in SPT for all foods contained in ADP101
- Quality-of-life changes over time using the following:
 - Food Allergy Quality of Life Questionnaire (FAQLQ)
 - Accidental exposure questionnaire
 - Immunotherapy-related quality-of-life (IQoL) questionnaire
 - 9-Item Treatment Satisfaction Questionnaire for Medication (TSQM 9)
 - Food Allergy Quality of Life–Parental Burden (FAQL-PB) questionnaire
- Proportion of subjects who develop confirmed new FAs to previously Non-reactive Foods at Screening as demonstrated by the Exit DBPCFC
- Incidence of AEs that lead to withdrawal from the study and/or discontinuation of study drug

- Incidence and shifts of clinically significant abnormalities in laboratory tests, vital signs, and spirometry forced expiratory volume in the first second (FEV1)/peak expiratory flow rate (PEFR)
- Frequency of allergic reaction AEs during treatment normalized for duration of treatment

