be extended to up to 8 weeks if a subject requires > 6 food challenges), it is considered a single visit per the study design. The visit and date corresponding to this portion will be taken directly as the Week 40 visit and date from the Suvoda IRT system for dosing dataset or the Week 40 visit from other data domains. The end date will be the date of the last Exit DBPCFC. During the Exit Food Challenge/Week 40 Visit period, the subject will keep taking their maintenance level of study drug except on days when it is specifically withheld for study procedures. For occurrence datasets such as adverse events and concomitant medications, the events or medications recorded with the start dates that falls into the start and end dates of this period, will be classified into this period. If the duration of these events span multiple periods, they will be considered ongoing safety events.

Adverse events during the Exit Food Challenge/Week 40 Visit period may be summarized by two periods: (a) Exit DBPCFC during challenge, i.e., days when Exit DBPCFC tests were administered and (b) Exit DBPCFC off challenge, i.e., days when Exit DBPCFC tests were not administered, in order to differentiate potentially treatment emergent vs potentially DBPCPC procedure-related event rates.

- **EOT:** This portion commences immediately after the Week 40 visit (the last Exit DBPCFC). Per the schedule of assessments, it covers an additional up to 4 weeks of daily blinded treatment after the last Exit DBPCFC until the subject completes treatment through the EOT visit. Although this portion spans over an up to 4 week period, it is considered a single visit per the study design. The visit and date corresponding to this portion will be taken directly as the EOT visit and date from either the Suvoda IRT system for doing dataset, or the EOT visit from other data domains. For occurrence datasets such as adverse events and concomitant medications, a start date of the last Exit DBPCFC plus 1 day and an end date using EOT eCRF date will be used to classify data into this portion. If the duration of these events span multiple periods, they will be considered ongoing safety events.

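### Whole-treatment allergic-TEAE, AESI and exposure-adjusted tables include reactions provoked by the Exit food challenge, so an ADP101 excess of dosing reactions can be diluted or, under some inputs, reversed in them

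*SAP*

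**What the plan says.** SAP Section 7.9.1 gives this definition of a treatment-emergent event: "any event that starts or worsens in severity on or after the first dose of study drug until 30 days after the last dose". SAP Section 3.1 adds: "Subjects will continue on study drug during the Exit DBPCFC period", with the daily dose withheld on challenge days. Reactions at the Exit challenge are therefore TEAEs, and the overview table confirms it with a row "Any TEAE due to food challenge".

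The same overview has rows for any allergic TEAE, "Any allergic TEAE with Grade ≥ 3" and any AESI, where AESI covers anaphylaxis, any event leading to epinephrine use, and EoE. Section 7.9.1 also plans allergic TEAEs by SOC and PT and by severity, and AESIs by category. It adds that "exposure adjusted incidence rates of TEAEs, treatment-emergent serious adverse events (TESAEs) and treatment-emergent AESIs will be presented", either per "total number of subject-years at risk during the study treatment period" or per dose received. No exclusion of challenge reactions is written for any of these.

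The SAP does separate challenge events elsewhere. Section 6.4.3 allows a split of the Exit period, one part being "Exit DBPCFC during challenge, i.e., days when Exit DBPCFC tests were administered", and Section 7.9 provides it for some AE summaries. SAP Section 4.4 lists the endpoint "Frequency of allergic reaction AEs during treatment normalized for duration of treatment".

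**The concern.** Allergic reactions to dosing are the main expected harm of oral immunotherapy. The Exit challenge is designed to provoke the same kind of event, and provokes it less often where treatment has worked. A whole-treatment allergic or AESI row therefore adds two things that point in opposite directions: dosing reactions, expected more often on ADP101, and challenge reactions, expected more often on placebo. A reader who takes that row as the comparison of dosing safety would see too small an excess on ADP101, or possibly none.

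The per-dose rate has a further mismatch. Challenge-day reactions enter the numerator on days when the dose is withheld and so add nothing to the denominator.

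**Working it through.** **Design figure.** The documents give no figure for challenge events in the safety tables. The relevant stated figure is the power of about 90% (SAP Section 3.2), which rests on 600-mg pass rates of 4% on placebo, 40% on low dose and 58% on high dose. Exact enumeration of the two-sided Fisher test, with 16 per active arm against 16 pooled placebo, gives 0.900 with Holm and 0.909 with Simes, so the figure reproduces. The implied failure rates are 96%, 60% and 42%.

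**Epinephrine-treated (AESI) incidence.** Whole-treatment incidence = 1 − (1 − d)(1 − c·f·e), taking dosing and challenge reactions as independent and one challenge per subject.
- d = dosing incidence: 7.7% active, 3.4% placebo. Protocol Section 2.3.2 gives these for the maintenance period of a peanut product, so they are illustrative only.
- c = share challenged; f = challenge failure rate.
- e = share of failed challenges leading to epinephrine. The documents do not give e, so a range is shown.

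With c = 1 and the 600-mg failure rates:

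| e | High dose | Low dose | Placebo |
|---|---|---|---|
| 0% | 7.7% | 7.7% | 3.4% |
| 5% | 9.6% | 10.5% | 8.0% |
| 10% | 11.6% | 13.2% | 12.7% |
| 20% | 15.5% | 18.8% | 21.9% |

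Example at e = 20%: high dose 1 − 0.923 × (1 − 0.42 × 0.20) = 15.5%; placebo 1 − 0.966 × (1 − 0.96 × 0.20) = 21.9%.

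Break-even: e = 0.043 / [c(0.966·f_placebo − 0.923·f_active)].
- c = 1, 600-mg rates: 8% (high dose), 12% (low dose).
- c = 1, with 80% or 90% of ADP101 and 100% of placebo reacting by 4000 mg: 19% or 32%.
- c = 0.8 in every arm: 10%, 14%, 24% and 40% for the same four cases.

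**Any allergic TEAE.** This uses the same formula with e = 1. Dosing incidences are assumed at 80% to 95% on ADP101 against 30% to 60% on placebo, a true gap of 30 to 50 points. The whole-treatment gap becomes −9 to 0 points if all are challenged, and +3 to +9 points if 80% are. Example with 90% against 60%, high-dose failure rates and c = 1: 1 − 0.1 × 0.58 = 94.2% against 1 − 0.4 × 0.04 = 98.4%.

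**Exposure-adjusted TEAE rate.** Assume one AE per failed challenge and 48 weeks (0.923 years) of treatment. One food then adds between (1.00 − 0.80)/0.923 = 0.2 and (0.96 − 0.42)/0.923 = 0.6 more placebo events per subject-year; five foods add 1.1 to 2.9. The order reverses only if the ADP101 dosing excess is smaller than this. The documents give no dosing event rate to compare it with.

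**What the other planned tables cover.**
- Repeated by period: the overall summary (including the any-allergic, Grade 3 or higher and AESI rows), AEs by SOC and PT, allergic TEAEs of Grade 3 or higher, AESIs by SOC and PT, and exposure-adjusted TEAE and AESI rates.
- Not on the by-period list: all-grade allergic TEAEs by SOC and PT, allergic TEAEs by severity, and AESIs by category.
- Exposure-adjusted list: TEAEs, related TEAEs, TESAEs, AESIs and related AESIs. Allergic TEAEs are absent, so the Section 4.4 endpoint has no such table.
- The during/off-challenge split is optional in Section 6.4.3 but promised for some summaries in Section 7.9.

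**The case against.** The strongest reply is that the safety package already separates the two sources. The overview with the disputed rows is repeated by period. There are challenge-attributed rows and a table of AEs due to food challenge, drug-related TEAE tables, and drug-related exposure-adjusted TEAE and AESI rates. SAP Section 7.8.3.6 reports epinephrine use at the Exit challenges apart from the dosing periods and, within those periods, by prompting event. Keeping every treatment-emergent event in the overall tables is a legitimate layout, and no table is designated as the lead one. Because the dose is withheld on challenge days, the calendar day is a reasonable classifier.

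This stands against the stronger reading that a reader might infer, namely that the ADP101 excess will be hidden or reversed. The documents do not support that:
- The dosing excess remains visible in the tables just listed.
- The direction depends on Exit epinephrine use, completion and dosing event rates that the documents do not give. With Exit epinephrine use of 5% on ADP101 and 8% on placebo, the row reads 12.3% against 11.1%, with no reversal.
- The failure rates are complements of responder rates at 600 mg, not AE rates. Protocol Section 9.4.3 counts dropouts as failures, and a responder can still react to another food or at 1000 to 4000 mg, which narrows the arm difference.

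The reply does not close the gap. Subject counts by period cannot be added up, because one subject may appear in several periods. The food-challenge row is not crossed with allergic status, grade or AESI, so it cannot be subtracted. No allergic-TEAE table is limited to drug-related events. A reaction starting the day after a challenge is classed as off-challenge, though how often that happens is unknown.

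**Conclusion.** The point holds in this form: the whole-treatment allergic-TEAE, AESI and exposure-adjusted tables mix dosing reactions with challenge reactions that the design expects more often on placebo, and no planned table gives whole-treatment allergic or AESI incidence without them. Dilution follows whenever provoked events are commoner on placebo. Reversal of the AESI row is plausible but conditional: it needs about 8% to 12% of failed challenges to lead to epinephrine at the 600-mg failure rates, and 19% to 32% if nearly all subjects react by 4000 mg, with everyone challenged once and dosing rates borrowed from another product. The missing exposure-adjusted table for the declared allergic-reaction endpoint needs no assumption. The other summaries reduce the risk of misreading but do not remove it. This should be corrected before unblinding; it affects descriptive safety output, not the primary analysis.

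**What to change.** In SAP Section 7.9.1:
- Keep all events in the total TEAE, SAE and AESI tables.
- Add challenge-excluded versions of the allergic TEAE tables (all grades, by severity, Grade 3 or higher), the AESI tables and the exposure-adjusted tables, using the due-to-food-challenge attribution that the overview already needs. Name these as the basis for comparing dosing safety between arms, and give the exposure-adjusted versions denominators that match their numerators.
- Add the exposure-adjusted rate of allergic TEAEs on the same basis.
- Make the during/off-challenge split definite, with the same wording in Sections 6.4.3 and 7.9, and use the attribution as a check on the calendar-day rule.

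The cost is SAP wording and a few extra tables, with no new data provided the attribution is recorded as the planned rows imply. The drawback is reliance on investigator attribution, which is made blind to treatment. Retaining the total tables ensures that no event disappears from the report.
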